## **MULTIFOCAL FITTING GUIDELINES**

### **1. Lens Selection**

- Update spectacle refraction and Add power.
- Determine dominance at distance vision by placing a +1.50 loose handheld trial lens alternatively over each eye binocularly through updated distance correction. The eye for which binocular vision is bluriest through the +1.50 is the dominant eye.
- Select lens distance prescription based upon spherical equivalent from spectacle prescription, adjusted for vertex distance if necessary.
- Choose trial lenses based upon the above calculation and select Add power (Both eyes).
  - . Bausch + Lomb INFUSE Multifocal Low Add: +0.75 to +1.50D
  - . Bausch + Lomb INFUSE Multifocal High Add: +1.75D to +2.50D

### **2. Lens Fitting**

- Allow lens to equilibrate for at least 10 minutes before assessing fit and vision.
- Evaluate distance and near vision binocularly in normal room illumination.
- If vision at distance and near is satisfactory, dispense lenses.

### **3. To Refine Near Vision**

If patient is wearing two Low Add lenses:

- Refinement 1: Place Bausch + Lomb INFUSE Multifocal High Add in non-dominant eye while keeping Bausch + Lomb INFUSE Multifocal Low Add in dominant eye.
- Refinement 2: If vision is still unsatisfactory, continue adding +0.25 at a time to the non-dominant eye using handheld lenses. Adjust contact lens power when vision is satisfactory.

If patient is wearing two High Add lenses:

- Refinement 1: Add +0.25D to the non-dominant eye.

- Refinement 2: If vision is still unsatisfactory, continue adding +0.25 D at a time to the non-dominant eye using handheld lenses.

#### **4. To Refine Distance Vision**

If patient is wearing two Low Add lenses:

- Refinement 1: Fit Bausch + Lomb INFUSE SVS in dominant eye while keeping Bausch + Lomb INFUSE Multifocal Low Add in non-dominant eye.
- Refinement 2: If vision is still unsatisfactory, add -0.25D at a time to dominant eye using handheld lenses. Adjust contact lens power when vision is satisfactory.

If patient is wearing two High Add lenses:

- Refinement 1: Fit with Bausch + Lomb INFUSE Multifocal Low Add in dominant eye while keeping Bausch + Lomb INFUSE Multifocal High Add in non-dominant eye.
- Refinement 2: If vision is still unsatisfactory, add -0.25 at a time to dominant eye using handheld lenses. Adjust contact lens power when vision is satisfactory.

#### **5. Patient Education**

All patients do not function equally well with multifocal correction. Patients may not perform as well for certain tasks with this correction as they have with multifocal reading glasses. Each patient should understand that multifocal correction can create a vision compromise that may reduce visual acuity and depth perception for distance and near tasks. During the fitting process it is necessary for the patient to realize the disadvantages as well as the advantages of clear near vision in straight ahead and upward gaze that multifocal contact lenses provide.

#### **WEARING SCHEDULE**

The wearing and daily disposable schedules should be determined by the eye care professional. Regular checkups, as determined by the eye care professional, are extremely important.

*Daily Disposable:*

There may be a tendency for the daily disposable subject to over-wear the lenses initially. Therefore, the importance of adhering to a proper, initial daily disposable schedule should be stressed to these subjects. The wearing schedule should be determined by the eye care professional. The wearing schedule chosen by the eye care professional should be provided to the subject. The lens is to be prescribed for single-use disposable wear and is to be replaced after each removal.

All subjects should be supplied with a copy of the Subject Instructions.

#### **HANDLING OF LENSES**

When lenses are dispensed, the subject should be provided with appropriate and adequate instructions and warnings for lens handling. The eye care professional should recommend appropriate and adequate procedures for each individual subject in accordance with the particular lens-wearing schedule.

## **CARE FOR A STICKING (NONMOVING) LENS**

If the lens sticks (stops moving), the subject should use a solution intended to lubricate or rewet a contact lens, as recommended by your eyecare practitioner. The subject should be instructed to not use plain water, or anything other than the recommended solutions. The subject should be instructed to contact the eye care professional if the lens does not begin to move upon blinking after several applications of the solution, and to not attempt to remove the lens except on the advice of the eye care professional.

## **REPORTING OF ADVERSE REACTIONS**

All serious adverse experiences and adverse reactions observed in subjects wearing the Bausch + Lomb daily disposable contact lens should be reported according to the Protocol.

## **HOW SUPPLIED**

The lenses are provided individually in a plastic blister containing sterile packaging solution. Each blister lid stock is marked with the following;

- Lens power
- Base curve
- Diameter
- ADD
- Lot number
- Expiration date
- Manufacturer's name
- Manufacturer's place of business
- Caution statement

3 LIST OF ABBREVIATIONS AND DEFINITIONS OF TERMS

Terms or Abbreviations	Definitions
ADE	Adverse Device Effect
AE	Adverse Event
ASADE	Anticipated Serious Adverse Device Effect
ATC	Anatomical Therapeutic Chemical
BSCVA	Best Spectacle Corrected Visual Acuity
D	Diopter
eCRF	Electronic Case Report Form
EDC	Electronic Data Capture
ePRO	Electronic Patient-Reported Outcomes
FAS	Full Analysis Set
GP	Gas Permeable
HIPAA	Health Insurance Portability and Accountability Act
ICF	Informed Consent Form
ID	Identification
logMAR	Logarithm of the Minimum Angle of Resolution
MedDRA	Medical Dictionary for Regulatory Activities
OD	Right Eye
OS	Left Eye
OU	Oculi Unitas; Both eyes used together
PMMA	Polymethylmethacrylate
PT	Preferred Term
SAE	Serious Adverse Event
SOC	System Organ Class
TEAE	Treatment-Emergent Adverse Event
USADE	Unanticipated Serious Adverse Device Effect
US	United States
VA	Visual Acuity
WHO DDE	World Health Organization Drug Dictionary Enhanced

Page 7 of 44 - CONFIDENTIAL

4 INTRODUCTION

This is a single-treatment study evaluating the product performance of a new silicone hydrogel multifocal daily disposable contact lens.

Approximately 300 subjects (600 eyes) will be enrolled in this 3-week, single-arm, bilateral, open-label study at approximately 20 investigative sites in the United States (US).

The study is designed to include habitual wearers of multifocal lenses. All subjects will be seen for a Screening/Dispensing Visit, at which time informed consent will be obtained and eligibility will be assessed.

All consented subjects will be assigned a subject identification (ID) number in sequential order by the Electronic Data Capture (EDC) system. At the Screening/Dispensing Visit, all eligible subjects will receive study contact lenses to wear on a daily disposable basis for approximately 3 weeks, with scheduled in-office follow-up visits at 1 week and 3 weeks.

No interim analyses are planned.

5 STUDY OBJECTIVES

The objective of this study is to evaluate the product performance of a new silicone hydrogel daily disposable multifocal contact lens, the Bausch + Lomb (kalifilcon A) Daily Disposable Multifocal Contact Lens, when worn by current soft contact lens wearers on a daily disposable wear basis.

6 INVESTIGATIONAL PLAN

6.1 Overall Study Design

Subjects will be fitted for their study multifocal lenses at a Dispensing Visit on study Day 1, at which screening procedures will also be performed. Subjects will return for a follow-up visit at 1 week and 3 weeks. At the 3-Week Follow-up Visit, subjects will be exited from the study.

The complete schedule of assessments in provided in Table 1.

Page 8 of 44 – CONFIDENTIAL

Table 1. Schedule of Assessments	Screening/ Dispensing Visit	1-Week Follow-Up Visit	3-Week Follow-Up Visit	Unscheduled	Exit
PROCEDURE/ASSESSMENTS	Day 1	Day 8	Day 23	Visit	Visit
		Day 6-10 (5-9 days after V1)	Day 20-26 (19-25 days after V1)		
Informed consent/HIPAA authorization	Х				
Demographics	Х				
Contact lens use history and contact lens use (e.g., average daily wear time, number of days worn, lens brand, lens wear modality, lens care system brand, product use history)	X (Habitual)	Xa	Xª		
Ocular medical history and concomitant medications	Х				
Changes in ocular medical history and concomitant medications	V	Х	X	X	Х
Eligibility	X	Tzh			
Lens fitting	X	Xb		Trh	
Dispense study materials	Х	Х		Xb	
Collect worn /unworn lenses, blister foils and study materials		Х	Х	X ^b	Х
Adverse events	X	Х	Х	v	Х
	Λ	Λ	Λ	Х	Λ
Symptoms/Complaints Form	X (Habitual)	Х	Х	Х	
Subject-completed forms/surveys		-	-		
Baseline Questionnaire	Х				
Lens Performance Rating Scales (after 10 minutes of lens settling & adaptation, if just inserted) ^d	Xc	Х	Х		
Instruct subject to complete Online Consumer Survey at least 7 days after the 1-					
Week Follow-Up Visit but before the 3- Week Follow-Up Visit		Х			
Confirm Visit in ePRO (triggers survey and reminders)		Х			
Confirm Subject has completed surveye			X		
With habitual lenses					
High-contrast distance logMAR lens VA (OU)	X				
Intermediate lens VA (OU)	X				
Near lens VA (OU)	X	 	l		
Without lenses	T			1	
Spherocylindrical refraction	X		ļ		Х
Near add power	Х				
High-contrast distance logMAR BSCVA (OD/OS/OU)	Х				Х
High-contrast intermediate logMAR BSCVA (OU w/near add)	Х				
High-contrast near logMAR BSCVA (OU w/near add)	X				

Table 1. Schedule of Assessments

Page 9 of 44 - CONFIDENTIAL

	Screening/ Dispensing Visit	1-Week Follow-Up Visit		Unscheduled	Exit
PROCEDURE/ASSESSMENTS	Day 1	Day 8	Day 23	Visit	Visit
Pupil measurement	Х				
Keratometry	Х				Х
Slit lamp exam	Х	Х	Х	Х	
With dispensed study lenses/With WORN s	tudy lenses				
High-contrast distance logMAR lens VA (OU)	Х	Х	Х	Х	Х
High-contrast intermediate logMAR lens VA (OU)	X	Х	Х	Х	Х
High-contrast near logMAR lens VA (OU)	Х	Х	Х	Х	Х
Lens wettability	Х	Х	Х	Х	Х
Lens deposits (type, percent, and degree)		Х	Х	Х	Х
Lens centration	Х	Х	Х	Х	Х
Lens movement	Х	Х	Х	Х	Х
Compare distance lens VA to screening/dispensing BSCVA	X	Х	Х	Х	Х
Investigator-completed forms					
Investigator questionnaire					Х

^a Collect only study lens wear at follow-up visits (average daily wear time, number of days worn, rewetting drop use, if a habitual rewetting drop user).

^b If the subject requires a change to their study lens power, adjust the fit and dispense study lenses with the appropriate power according to the Fitting Guide.

^c All Lens Performance ratings will be collected on habitual lenses at Screening. Abbreviated Lens Performance ratings will be collected once the study lenses are dispensed and adapted on the eye. Use provided rating scales (separate document).

^d At dispensing allow 10 minutes from insertion for lens settling & adaptation before performing assessments.

^e If subject has not completed survey, they should complete at this visit.

Note: All VA measurements MUST be made using a phoropter.

Note: If this is an Exit Visit, also perform the procedures listed under the Exit Visit column.

6.2 Selection of Study Population

To be eligible for entry into the study, the subject must meet the following inclusion criteria:

- 1. Subjects must be age 40 years or older on the date the ICF is signed and have the capacity to provide voluntary informed consent.
- 2. Subjects must be willing and able to comply with all treatment and follow-up/study procedures, as well as willing and able to refrain from using any contact lenses other than those provided for the duration of the study.
- 3. Subjects must be correctable through spherocylindrical refraction to 42 letters (0.1 logMAR) or better (distance, high contrast) in each eye.
- 4. Subjects must have clear central corneas and be free of any anterior segment disorders.
- 5. Subject must wear their current lenses for a minimum of 12 hours per day at least four days per week.

Page 10 of 44 – CONFIDENTIAL

- 6. Subjects must habitually wear a multifocal lens in each eye.
- 7. Subjects must be an adapted multifocal soft contact lens wearer for a minimum of 6 months.
- 8. Subjects must require distance lens correction from +3.00 to -6.00 D in each eye.
- 9. Subjects must be presbyopic and require near add correction from +0.75 to +2.50 D in each eye.
- 10. Subjects must have access to an internet connection to complete an online survey and be able to receive text message.

The subject is not eligible to participate in the study if the subject meets any of the following exclusion criteria:

- 1. Subjects participating in any drug or device clinical investigation within 30 days prior to entry into this study and/or plan to do so during the period of study participation.
- 2. Subjects who are women of childbearing potential (those who are not surgically sterilized or postmenopausal) are excluded from participation in the investigation if they meet any one of the following conditions:
 - She is currently pregnant
 - She plans to become pregnant during the study
 - She is breastfeeding
- 3. Subjects with any systemic disease currently affecting ocular health or that, in the Investigator's opinion, may have an effect on ocular health during the course of the study.
- 4. Subjects with an active ocular disease.
- 5. Subjects who have had any corneal surgery (e.g., refractive surgery).
- 6. Subjects who have worn gas-permeable (GP) contact lenses within the last 30 days or who have worn polymethylmethacrylate (PMMA) lenses within the last 3 months.
- 7. Subjects who currently wear monovision or toric contact lenses.
- 8. Subjects who are not correctable to 32 letters (0.3 logMAR) with bilateral soft multifocal contact lenses.
- 9. Subjects with an ocular astigmatism >1.00 D in either eye.
- 10. Subjects with anisometropia (spherical equivalent) >2.00 D.
- 11. Subjects with any Grade ≥2 finding during the slit lamp examination. Subjects with corneal infiltrates of ANY GRADE are not eligible.
- 12. Any "Present" finding during the slit lamp examination that, in the Investigator's opinion, interferes with contact lens wear.
- 13. Any scar or neovascularization within the central 6 mm of the cornea. Subjects with minor peripheral corneal scarring (that does not extend into the central area) that, in the Investigator's opinion, does not interfere with contact lens wear are eligible for this study.

Page 11 of 44 – CONFIDENTIAL

- 14. Subjects who are amblyopic.
- 15. Subjects using any systemic or topical ocular medication that will, in the Investigator's opinion, affect ocular physiology or lens performance.
- 16. Subjects who are allergic to any component in the study care products.

If a subject meets all the inclusion criteria and does not exhibit any of the exclusion criteria, the subject is eligible for entry into the study. Ineligible subjects MUST NOT be enrolled in this study. Any subject enrolled in the study who later is found to have not met the eligibility criteria at entry will be discontinued.

6.3 Treatments

Subjects will be assigned to the Bausch + Lomb (kalifilcon A) Daily Disposable Multifocal Contact Lens, manufactured by Bausch & Lomb Incorporated, Rochester, NY.

The description of the Test lens is as follows:

- Sphere power: -6.00 D to +3.00 in steps of 0.25 D
- Add: High and Low
- Diameter: 14.2 mm
- Base curve: 8.6 mm
- Material: kalifilcon A
- Packaging solution: phosphate-buffered saline solution

6.4 Efficacy and Safety Variables

6.4.1 Efficacy Variables

The primary endpoint will be assessed as the proportion of subjects agreeing with the statement "Clear vision: near, far, and in-between" in the online consumer survey, which is completed at least 7 days after the 1-Week Follow-Up Visit but before the 3-Week Follow-Up Visit.

Supportive effectiveness will include the following:

- Consumer survey
- Investigator questionnaire
- Number of visits to achieve a successful fit
- Number of lenses to achieve a successful fit
- Contact lens visual acuity (VA) in logarithm of the minimum angle of resolution (logMAR) units
- Contact lens VA in Snellen equivalent units
- Lens performance rating scales
- Lens deposits

Page 12 of 44 - CONFIDENTIAL

- Lens characteristics
 - o Wettability
 - \circ Centration
 - o Movement

6.4.2 Safety Variables

The following variables will be used to evaluate safety:

- Adverse events (AEs)
- Clinical safety examinations
 - o Symptoms/complaints
 - Slit lamp examination
 - o Best spectacle corrected visual acuity (BSCVA) in logMAR units
 - o BSCVA in Snellen equivalent units
 - o Spherocylindrical refraction
 - o Keratometry

6.5 Statistical Methods

6.5.1 Data Sets Analyzed

The Full Analysis Set (FAS) will consist of all eligible, dispensed subjects or eyes. If only one eye is dispensed, the subject will be included in the FAS for subject level analyses, but only the dispensed eye will be included in the FAS for eye level analyses. The FAS will be used for all efficacy analyses in subject level and eye level data.

The Safety Analysis Set will consist of all dispensed subjects or eyes. If only one eye is dispensed, the subject will be included in the Safety Analysis Set for subject level summaries, but only the dispensed eye will be included in the Safety Analysis Set for eye level summaries. All safety analyses and summaries will be based on the Safety Analysis Set.

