#### **4.1 Description of Investigational Test Article (Test)**

The Test lens to be used in this study is the Bausch + Lomb (kalifilcon A) Daily Disposable Multifocal Contact Lens, manufactured by Bausch & Lomb Incorporated, Rochester, NY. The description of the Test lens is as follows:

- Sphere power: -6.00 D to +3.00 in steps of 0.25 D
- Add: High and Low
- Diameter: 14.2 mm
- Base curve: 8.6 mm
- Material: kalifilcon A
- Packaging solution: phosphate-buffered saline solution

The investigational test article(s) for this study are manufactured and verified under a controlled process according to the applicable regulations. With regard to those aspects, every precaution has been taken to protect the health and safety of study participants. per B&L SOP TD-GEN-FRM-039 Clinical Scorecard Evaluation

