i. Perform a slit lamp examination. Record all slit lamp findings and at a minimum sketch the following in the subject's source document:

- Any ungraded finding marked as “PRESENT”
- Any corneal scars
- Any corneal staining
- Any corneal infiltrate
- Any other graded slit lamp findings Grade >2

j. Assess eligibility. Indicate on the Screening Log whether the subject is a “Screen Pass” or “Screen Fail.” “Screen Fail” subjects are ineligible and cannot be enrolled in the study. The reason for screen failure must be documented on the Screening Log and in the subject record and maintained with a copy of their ICF.

k. Administer the Baseline Questionnaire.

l. Dispense 10 study contact lenses per eye according to the Fitting Guide and dispense all study materials.

- **The subject MUST insert the study lenses at this visit.**

*Note: Study lenses should be allowed to equilibrate a minimum of 10 minutes on the eye. Subjects should be encouraged to walk around, read, and/or look outside while the lens is equilibrating. If the vision is unsatisfactory, the lenses should be refined by adding add power according to the fitting guide to achieve acceptable vision. Number of refinements completed to achieve satisfactory vision in each eye will need to be collected.*

- Order remaining study contact lenses on Stock Material Order Form.

m. For the dispensed lenses, perform the following assessments:

- Dispensed lens sphere power
- Dispensed lens add power (high, low, or none)
- Distance (OU), intermediate (OU), and near (OU) lens VA
- Lens wettability
- Lens centration
- Lens movement

n. Compare the high-contrast OU distance lens VA to the high-contrast OU distance BSCVA obtained at this visit. If the VA has decreased by  $\geq 10$  letters, explain.

- o. Have the subject complete the abbreviated Lens Performance Rating Scales for study lenses using the 0-100 rating scales provided by the Sponsor.
- p. Collect/assess all AEs/ADEs, including serious or significant non-serious AEs.
- q. Provide instructions for study contact lens wear to the subject and instruct the subject to wear their study lenses to the 1-Week Follow-Up Visit.
- r. Register subject information in ePRO system **while subject is in office**. This should be done only for eligible, dispensed subjects. Subject data to be entered for registration:
  - Subject number
  - Date of birth
  - Subject phone number (text capability)
  - Screen date

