***Note: All VA measurements MUST be made using a phoropter.***

- a. Collect changes in ocular medical history and concomitant medications
- b. Collect the following study lens information from the subject:
  - Over the last week, Average number of days per week worn
  - Over the last week, Average daily wearing time, hours per day
  - Over the last week, Average hours of comfortable wear per day
  - Hours lenses worn on the day of this visit
  - Over the last week, average number of times used rewetting drops per day. (Note: Only to be completed by subjects reporting rewetting drop use with habitual lenses at the Dispensing Visit.)
- c. Collect the Lens Performance Ratings for dispensed contact lenses using the 0-100 rating scales provided by the Sponsor.
- d. Collect the Symptoms/Complaints for dispensed lenses.
- e. If the subject did not come to the visit wearing one or more study lenses, go to step g. Otherwise, evaluate the study lenses (while on eye) and record the following assessments:
  - Distance (OU), intermediate (OU), and near (OU) lens VA
  - Lens wettability
  - Lens deposits (type, percent, and degree)

- Lens centration
- Lens movement

Compare the high-contrast OU distance lens VA to the high-contrast OU distance BSCVA obtained at the Screening/Dispensing visit. If the VA has decreased by  $\geq 10$  letters, explain.

f. If the subject requires a change to their study lens power at the 1-Week Follow-Up Visit, collect the worn lenses from the subject, and the unworn lenses for the eye(s) requiring a change, adjust the lens power, dispense study lenses with the appropriate power according to the Fitting Guide, and perform assessment in step e, (with exception of deposits), after an equilibration time of 10 minutes.

***Note: Study lenses should be allowed to equilibrate a minimum of 10 minutes on the eye. Subjects should be encouraged to walk around, read, and/or look outside while the lens is equilibrating. If the first set of study lenses is unacceptable to the subject, adjust study lenses according to the Fitting Guide to achieve acceptable vision. Continue to adjust until vision is acceptable. Allow the study lens(es) to equilibrate a minimum of 10 minutes on the eye before conducting the assessments in step e. Number of refinements completed to achieve satisfactory vision in each eye will need to be collected.***

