#### **5.1.5 Unscheduled Visits**

Additional visits may be scheduled, as necessary, to ensure the safety and well-being of subjects. All additional exams should be fully documented in the source documents and on Unscheduled Visit eCRFs, as appropriate. Visits intended to fulfill scheduled visit requirements that fall outside the designated scheduled visit range, are not Unscheduled Visits. In these cases, the visit data will be collected and transcribed to the appropriate scheduled visit eCRF.

If a subject is seen for multiple visits during a given visit timeframe, the data from the visit that is intended to meet the protocol requirements for the scheduled visit should be captured on the visit eCRF. Where such a determination cannot be made, the first visit within the scheduled visit interval will be used for completion of the protocol required scheduled visit eCRF. Data from any additional visits within a scheduled visit interval will be captured on an Unscheduled Visit eCRF.

If a subject is only seen for replenishment of study lenses, a complete exam is not required, as long as the subject is not experiencing any problems. If study lenses are replaced, record

the eye, dispensed lens sphere power, add power (high, low, none), and primary replacement reason in the Product Dispensing Only eCRF. Collect worn study lenses from the subject. Record the eye, lens type, add power, sphere power, lot number, and quantity dispensed in the Product Accountability Log.

Subjects who require further follow-up on an AE/SAE upon discontinuation or at the conclusion of the 3-Week Follow-Up Visit will be followed according to the Post-study Follow-up [Section 3.3.4](#). At these follow-up visits, the subject should remove contact lenses s/he may be wearing. Assessments will be performed according to the investigator's judgement. The Investigator is required to follow the subject until the condition no longer warrants further follow-up for study purposes.

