***Note: If the subject is experiencing problems, complete the entire Unscheduled Visit Form.***

- b) Collect the following information from the subject regarding study lenses:
  - Average number of days per week worn
  - Average daily wearing time, hours per day
  - Average hours of comfortable wear per day
  - Hours lenses worn on the day of this visit
  - Rewetting drop use.
- c) Collect Symptoms/Complaints.
- d) If the subject did not come to the visit wearing one or more study lenses, go to step e. Otherwise, evaluate the study lenses (while on eye), and record the following assessments:
  - Distance (OU), intermediate (OU), and near (OU) lens VA
  - Lens wettability
  - Lens deposits
  - Lens centration
  - Lens movementCompare the high contrast OU distance lens VA to the high contrast OU distance BSCVA obtained at the Screening/Dispensing Visit. If the VA has decreased by  $\geq 10$  letters or more, explain.
- e) Perform a slit lamp examination (remove the lenses if the subject wore lenses to the visit). Record all slit lamp findings and at a minimum sketch the following in the subject's source document:
  - Any ungraded finding marked as "PRESENT"
  - Any corneal scars
  - Any corneal staining
  - Any corneal infiltrate
  - Any other graded slit lamp findings Grade  $>2$
- f) If an unscheduled lens replenishment for the same lens is required, dispense additional lenses, and collect the following:
  - Primary reason for replacement

- Dispensed lens sphere power
- Dispensed lens add power (high, low)
- Distance (OU), intermediate (OU), and near (OU) lens VA
- Lens wettability
- Lens centration
- Lens movement

**Note:** *Remember to record replenishment on the Product Accountability Log.*

**Note:** *The Investigator must return all worn and unworn study lenses to the Sponsor in the return materials provided. All study contact lenses must be accompanied by a Product Accountability Log.*

- If an unscheduled lens replacement requires a change in lens power for unacceptable vision, follow steps f, g, h, and i in [Section 5.1.2](#).
- The Unscheduled Visit eCRFs should be completed.

If the subject is discontinued or exited at this visit, complete the Exit Visit eCRFs.

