6.5.10.5.4 Number of Refinements to Achieve a Successful Fit

The number of refinements completed will be collected at Screening/Dispensing Visit and 1-Week Follow-up Visit (if subject requires a change to their study lens power at this visit) at eye level. Data will be summarized for the FAS as continuous summary statistics at the eye level. Refinements at the Screening/Dispensing Visit and the 1-Week Follow-up Visit will be summarized separately, and a combination of the two visits will be summarized as well.

The number of lens refinements at the Screening/Dispensing Visit will be summarized by baseline add groups using categorical summary statistics for the following categories: 1, 2, 3, >3 refinements. The summary will be at the eye level. Baseline add group is defined based on the add power obtained at the Screening/Dispensing Visit (> 1.50D as High Add, <= 1.50D as Low Add). A total column combining low add and high add will be summarized. Eyes with missing add will not be included in this analysis.

Starting lens sphere and add as well as final lens sphere and add for dispensed lenses at the Screening/Dispensing Visit will also be summarized by baseline add groups. If the subjects achieve plano status with their starting sphere and add for an eye, no final sphere and add will be collected and the starting sphere and add will be summarized as their final sphere and add.

If the subject requires a change to their study lenses at the 1-Week Follow-up Visit, then the final sphere and add at the Screening/Dispensing Visit and 1-Week Follow-up Visit will be summarized. An additional summary of final add on both eyes will be conducted by the following categories: Low add – Low add, Low add – None, Low add – High add, High add – High add – None. Percentages will be based on the number of subjects with non-missing responses for both eyes at each visit. Final sphere and add for this analysis are the final dispensed lens power that can provide satisfactory vision after the fitting procedure (final sphere and add for subjects whose starting sphere and add cannot achieve satisfactory vision and starting sphere and power for subjects who have satisfactory vision with starting lens power).

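### Should the primary endpoint also be reported by the lenses actually dispensed, and is "dispensed" defined clearly enough to fix the Full Analysis Set?

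*SAP*

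**What the plan says.** Protocol 4.1 and SAP 6.3 describe the test lens with "Add: High and Low". Protocol 4.0 lists dispensing sets of INFUSE lenses among the study materials, separately from the test multifocal. For a subject in two Low Add lenses whose distance vision needs refining, Appendix D says: "Refinement 1: Fit Bausch + Lomb INFUSE SVS in dominant eye while keeping Bausch + Lomb INFUSE Multifocal Low Add in non-dominant eye".

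The data forms allow for this. Protocol 5.1.1 step m records "Dispensed lens add power (high, low, or none", and Protocol 5.1.5 records "add power (high, low, none), and primary replacement reason in the Product Dispensing Only eCRF". Step f of the unscheduled visit, which covers replenishment of the same lens, has only "Dispensed lens add power (high, low". At the 1-Week Visit the site may "adjust the lens power, dispense study lenses with the appropriate power according to the Fitting Guide".

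On analysis, SAP 6.5.10.5.4 states that "An additional summary of final add on both eyes will be conducted by the following categories", and those categories include a Low Add lens paired with none. It also tabulates add changes to and from none. SAP 6.5.11.5 breaks survey agreement down by baseline refraction add, not by the lens supplied.

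The primary analysis uses the FAS: "The Full Analysis Set (FAS) will consist of all eligible, dispensed subjects or eyes". Neither document says at what moment a lens counts as dispensed. Protocol 5.1.1 places dispensing at step l and assesses the dispensed lenses at step m. Appendix D has lenses dispensed once fit and vision are satisfactory.

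**The concern.** There are two worries.

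**Lens worn.** The objective names the multifocal lens, and the entry criteria are built around a multifocal in each eye. If some subjects leave with a non-multifocal lens in one eye, the pooled agreement rate describes a fitting system rather than the bilateral test lens. A reader of the tables could not see how the bilateral group answered. The baseline-add subgroup does not fill the gap, because a subject with a low baseline add may leave with two multifocals or with one plus an add-none lens.

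**FAS membership.** If lenses are dispensed at step l, a subject whose vision stays unacceptable is in the FAS and, with no survey answer, counts as Disagree in the worst-case analysis. If they are dispensed only after a satisfactory fit, the same subject is outside both.

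**Working it through.** **The plan's own figure.** Inputs from SAP 6.5.13: n = 270, null 0.5, alternative 0.6, one-sided 5% exact binomial test. The smallest r with P(X ≥ r | 270, 0.5) ≤ 0.05 is 150 (p = 0.0387; 149 gives 0.0501). P(X ≥ 150 | 270, 0.6) = 0.939, which agrees with the stated 93%.

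**Lens worn: how far could the bilateral group differ?** Suppose 162 of 270 agree (60%) and m subjects have an add-none eye. The documents give no value for m, so a range is assumed. If all m agreed, the bilateral rate is (162 − m)/(270 − m). If none did, it is 162/(270 − m).

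| m | All m agree | None agree |
|---|---|---|
| 10 | 152/260 = 58.5% | 162/260 = 62.3% |
| 27 | 135/243 = 55.6% | 162/243 = 66.7% |
| 54 | 108/216 = 50.0% | 162/216 = 75.0% |

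These are arithmetic extremes and not likely outcomes.

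**What the extra table would show.** With both groups agreeing at about 60%, the Clopper-Pearson 95% intervals are:

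| m | Add-none group | Bilateral group |
|---|---|---|
| 10 | 6/10 (26.2% to 87.8%) | 156/260 (53.8% to 66.0%) |
| 27 | 16/27 (38.8% to 77.6%) | 146/243 (53.6% to 66.3%) |
| 54 | 32/54 (45.0% to 72.4%) | 130/216 (53.3% to 66.8%) |

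The add-none group would be too small to separate from the other.

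**Could pooling mislead the test?** Suppose bilateral subjects agree at exactly 0.5, and 20% of subjects have an add-none eye and agree at 0.7. The pooled rate is 0.8 × 0.5 + 0.2 × 0.7 = 0.54, and the test rejects with probability 32%. For the population as fitted this is no false positive, since 0.54 exceeds 0.5. It would mislead only someone who took the result to describe bilateral wear alone.

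**FAS membership: the passages side by side.** Step l tells the site to follow the Fitting Guide when dispensing, and the note on equilibration and refinement stands under that same step. Step l therefore takes in Appendix D's condition, and the lenses assessed at step m are those left after refinement. Non-dispensed is a status on the Subject Exit Form (Protocol 5.1.4 step a). Step r of 5.1.1 restricts ePRO registration to eligible, dispensed subjects. Someone recorded as non-dispensed should therefore have no survey answer, and a missing answer is not imputed in the primary analysis.

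**Size in the worst-case analysis.** Take 270 non-neutral answers and no other losses, and add k disputed subjects as Disagree.

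| k | Agreements needed | Results that would lose significance |
|---|---|---|
| 0 | 150 of 270 | none |
| 3 | 151 of 273 | 150 only |
| 5 | 152 of 275 | 150 to 151 |
| 10 | 155 of 280 | 150 to 154 |

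At the planned 60% (162/270), 25 such subjects would be needed (162/295, p = 0.0514). The plan allows for 300 − 270 = 30 losses of every kind. Losses among dispensed subjects are already counted as Disagree in the planned worst case.

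**The case for a change.** The strongest case for acting is that the table costs almost nothing. Dispensed add is already collected and the sponsor evidently expects add-none eyes. Fixing the grouping in advance would also prevent a later choice of whichever split looks best. It is correct that no planned table crosses the primary endpoint with the dispensed lens, and that the baseline-add subgroup answers a different question.

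The value of the table is limited all the same. Under the Fitting Guide the SVS lens goes to subjects in two Low Add lenses whose distance vision was not good enough. Restricting to bilateral multifocal wear therefore removes some of the harder fits, and any difference between the groups mixes the lens with the eye. The FAS as fitted is the less selected summary. Anyone who wants the cross-tabulation can build it from planned listings 16.2.4.7.1, 16.2.5.1 and 16.2.6.2.

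On dispensing, it is fair to say that the term is undefined and the sequence is not spelled out. That is a gap in wording, which an analyst would close from the recorded exit status and the dispensation listing. Adding non-dispensed subjects to the worst case as Disagree would put people outside the FAS into an FAS table. It would also score a survey opinion for people who did not take the lens home.

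**Conclusion.** No change to the plan follows. The missing breakdown is a fair trade-off: the plan reports the fitted population and describes the lenses separately, while a split made after fitting would be imprecise and confounded. The undefined term is a gap that analysts can fill sensibly, and it leaves the primary test as it is. Its reach is confined to the worst-case and tipping-point analyses of a result close to 150 of 270.

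Two differences in wording remain and should be reconciled when the documents are next edited: the description of the test lens against the Fitting Guide, and the add categories in the two unscheduled-visit passages. Both are clerical and alter no analysis.

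This rests on three assumptions. The share of add-none subjects is unknown and was taken as 10 to 54 of 270. SVS is not spelled out and is inferred to be the add-none lens. Few eligible subjects are expected to go undispensed for vision or fit, since exclusion criterion 8 already removes those not correctable to 32 letters with bilateral multifocals.
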